7.1.3 From randomization to stabilization

Once the baby's eligibility to take part in the study is confirmed, the Investigator will randomize the baby to the assigned treatment by using the IRT system. Pharmacological treatment will start up to 7 days after delivery in neonates who show signs of NOWS and have failed to respond to non-pharmacologic care.

All neonates enrolled in the study should receive routine cardiorespiratory monitoring using continuous 3-lead ECG and pulse oximetry. This should commence before the first dose of study drug (CHF6563 or morphine) is administered and continue throughout the dose-escalation phase, stabilization phase and the initial stage of the weaning phase. During the later stages of weaning, the continuous ECG monitoring may be discontinued at the investigator's discretion, to allow nonpharmacological care strategies to be maximized.

If an abnormal rhythm is detected by the continuous 3-lead ECG, the neonate should be evaluated with a 12-lead ECG and dosing interrupted. If a pediatric cardiologist confirms a QTc interval of ≥ 500 ms on a 12-lead ECG, the study treatment should be discontinued.

The following procedures will take place only at randomization:

- Inclusion/ exclusion criteria
- Randomization: neonates with a GA ≥ 36 weeks and the sum of 3 consecutive FNAST assessment scores ≥ 24 or a single score ≥ 12 will be assigned in a 2:1 ratio to either CHF6563 or morphine. Treatment doses will be calculated according to birth weight which should be rounded to the second decimal place.

The following procedures will take place from randomization to stabilization:

- NOWS score: FNAST will be used to assess withdrawal signs. Signs of withdrawal will be assessed and recorded every 4 hours (± 1 hour)
- Vital signs: heart rate (HR), respiratory rate (RR), peripheral oxygen saturation (SpO_2), and body temperature (BT) will be collected at the same time of the NOWS score, except for BT which will be collected at least once per day. Blood pressure (DBP; MBP; SBP) will be recorded if collected according to site clinical practice. Routine cardiorespiratory monitoring will be performed using continuous 3-lead ECG and pulse oximetry.
- Body weight – all body weights recorded as part of standard of care will be collected (minimum requirement - once a week)
- Treatment administration: treatment doses will be calculated according to birth weight (which should be rounded to the second decimal place) and the NOWS score which will be assessed and recorded every 4 hours.
- Feeding status: breastfeeding, formula feeding, mixed feeding, and the proportion of maternal breastmilk intake during this period of time i.e. randomization to stabilization will be recorded.
- Liver function test (AST, ALT): will be performed after first dose and following treatment stabilization prior to the first weaning dose and recorded.
- Blood sampling for CHF6563 pharmacokinetics will be performed.
- Further concomitant medications/procedures and adverse events as well as changes in those already reported will be recorded.

Clinical Study Code No.: CLI-06563AA1-02	Version No.: 6.0
IND No.: 131,339	Date: 18 March 2021

7.1.4 From weaning to the end of treatment

The following procedures will take place:

- NOWS score: signs of withdrawal will be assessed and recorded every 4 hours (± 1 hour) using FNAST
- Vital signs: heart rate (HR), respiratory rate (RR), peripheral oxygen saturation (SpO_2), body temperature (BT) will be collected at the same time of the NOWS score but only once a day. Blood pressure (DBP; MBP; SBP) will be recorded if collected according to site clinical practice. Cardiorespiratory monitoring will be continued during the initial stage of weaning and can be discontinued at the investigator's discretion during later stage.
- Body weight – all body weights recorded as part of standard of care will be collected (minimum requirement - once a week).
- Treatment administration: treatment doses will be calculated according to birth weight (which should be rounded to the second decimal place) and the NOWS score which will be assessed and recorded every 4 hours.
- Feeding status: breastfeeding, formula feeding, mixed feeding, and the proportion of maternal breastmilk intake during this period of time i.e. weaning to end of treatment will be recorded.
- Blood sampling for CHF6563 pharmacokinetics will be performed.
- Further concomitant medications/procedures and adverse events as well as changes in those already reported will be recorded.

7.1.5 End of treatment period Visit (48 hours ± 4 h after the last dose)

The following procedures will take place:

- NOWS score
- Vital signs: heart rate (HR), respiratory rate (RR), peripheral oxygen saturation (SpO_2), body temperature (BT), will be collected; blood pressure (DBP; MBP; SBP) will be recorded if collected according to site clinical practice
- Head circumference, and body weight and length
- General physical and neurological examination
- Liver function test (AST, ALT) will be performed and recorded
- Feeding status: breastfeeding, formula feeding, mixed feeding, and the proportion of maternal breastmilk intake during this period of time i.e. end of treatment to discharge will be recorded.
- Further concomitant medications and adverse events as well as changes in those already reported.

7.1.6 Functional unblinding

The weaning period requires a lower number of weaning steps for CHF6563 compared to morphine. In order to avoid maintaining babies randomized to CHF6563 in the hospital following completion of study drug, only to receive placebo for several days (about 5, depending on the severity of the withdrawal), the unblinded pharmacist will advise the clinical staff that the baby has completed active study treatment following the last active dose of CHF6563 and babies will be eligible for discharge (at least insofar as the clinical trial is concerned) 48 hours after the last active dose. Since the cessation dose will not occur at the same weaning step for the 2 treatment arms, it will be possible to ascertain the treatment for each baby after the weaning step which corresponds to the cessation dose of CHF6563. This is considered a "functional

Clinical Study Code No.: CLI-06563AA1-02	Version No.: 6.0
IND No.: 131,339	Date: 18 March 2021

unblinding” since, after this point, it will be possible for members of the blinded team to ascertain the treatment arm.

Prior to the last scheduled dose of CHF6563, all members of the blinded study team will remain completely blinded. Following the last scheduled dose of CHF6563/placebo, members of the blinded study team will not have access to the explicit treatment codes, but it will be possible to ascertain the treatment arm. Similarly, data review will occur without access to explicit treatment codes, since the explicit treatment codes will be maintained in a confidential manner. The randomization list and explicit treatment codes will be disclosed to blinded study team members only after the database is locked.

7.1.7 Follow-up

Regular follow up will continue both before and after discharge from the hospital to identify those babies who suffer recurrence of significant withdrawal.

- During the first 7 days after the initial 48 hours observation period following the last dose:
 - a) If the baby has already been discharged from the hospital, daily telephone contact with the primary caregiver (parental/legal guardian or foster mother). The following information will be recorded:
 - General well-being
 - Escalation of withdrawal signs
 - Feeding status: breastfeeding, formula feeding or mixed feeding
 - Further concomitant medications and adverse events as well as changes in those already reported.
 - b) If the baby stays in the hospital, the following information will be recorded:
 - General well-being
 - Escalation of withdrawal signs
 - Feeding status: breastfeeding, formula feeding, mixed feeding, and the proportion of maternal breastmilk intake during this period of time i.e. first 7 days.
 - Further concomitant medications and adverse events as well as changes in those already reported.
- From 10 days and until 6 weeks after the last treatment dose, weekly telephone contact with the primary care will continue. The following information will be recorded:
 - General wellbeing
 - Escalation of withdrawal signs
 - Feeding status: breastfeeding, formula feeding or mixed feeding
 - Further concomitant medications and adverse events as well as changes in those already reported.

7.1.8 Follow-up: 18 months (± 1 months)

A further clinical assessment at 18 months (± 1 months) will be performed by a multidisciplinary team at the participating study centers to assess the general wellbeing, growth and long-term neurodevelopmental assessment and growth parameters.

The clinical assessment will collect information on the following domains:

Clinical Study Code No.: CLI-06563AA1-02	Version No.: 6.0
IND No.: 131,339	Date: 18 March 2021

- Health status (general medical history and physical examination, including growth parameters, medical illness, developmental issues, medications and hospital admission)
- Environmental / social factors (foster care, domestic violence exposure, substance use / treatment)
- Cognitive and behavioral development (Bayley Scales of Infant Development – all 5 domains)
- Assessments of the mother / primary carer using standardized questionnaires (e.g. Brief Symptom Inventory (BSI), Quick Inventory of Depressive Symptomatology (QIDS), Parenting Stress Index (PSI), Child Behavior Checklist (CBCL))

This 18-month clinical assessment will be analyzed and evaluated separately from the initial part of the study and be object of an addendum to the initial core clinical study report. Individual assessments will be described in more detail in an additional document.

7.2 Investigations

7.2.1 NOWS score

FNAST (refer to [APPENDIX 4 – Finnegan Neonatal Abstinence Scoring Tool \(FNAST\)](#)) will be used to assess the severity of NOWS.

Details on FNAST, training package and site validation will be provided in a separate report document.

7.2.2 Feeding Status

Feeding status will be collected daily from the electronic patient record. (Formula /breast milk or a mixed feeding and proportion of maternal breast milk intake).

7.2.3 Toxicological collection

It will only be performed in those hospitals where this is common clinical practice, according to site procedures.

7.2.4 Vital signs

At screening and from the randomization until the end of the treatment, heart rate (HR), respiratory rate (RR), peripheral oxygen saturation (SpO₂), body Temperature (BT) will be collected. Blood pressure (DBP; MBP; SBP) will be recorded if collected according site clinical practice.

From randomization up to the stabilization they will be collected at the same time of the NOWS score, except for BT which will be collected at least once per day.

From weaning until the end of the treatment they will be collected once a day at the time of NOWS score.

Cardiorespiratory monitoring using continuous 3-lead ECG and pulse oximetry should be performed during treatment (starting before the first dose of study drug and continuing up to the initial stage of the weaning phase).

7.2.5 Hematology/blood chemistry and liver function

The results of investigations - if performed according to site clinical practice - prior to randomization will be recorded; these can include full blood count (FBC), urea, creatinine and electrolytes (sodium, potassium, magnesium, calcium, phosphorus), glucose, C-reactive protein.

Liver-function test analysis (aspartate aminotransferase [AST], alanine aminotransferase [ALT],) will be performed on 3 occasions: after the first dose, at stabilization and 48 hours (± 4 h) after the last treatment dose.

7.2.6 Pharmacokinetics

Blood sampling for PK will occur the day of randomization and then every 5 ± 1 day until the last dose. The first blood sampling should be taken after the first dose. Subsequent sampling should occur after the morning dose and be timed to fit in with the following sampling windows: one blood sample should be taken in the 0-2 h post-dose time window, one in the 2-4 h post-dose time window and one in the 4-8 h post-dose time window.

If possible, in order to minimize discomfort for the babies, PK samples should be collected simultaneously to routine blood sample collection.

Twenty μ l aliquot of blood will be spotted onto DMPK-A cards and allowed to dry at room temperature on an open non-absorbent surface for at least two hours (at least three spots per sample). Cards will be then stored at room temperature in a sealed plastic bag containing desiccant until shipment to the central Laboratory for determination of CHF6563.

Around 300-360 μ l will be collected every 5 ± 1 day until end of last dose.

[REDACTED] is allocated as reference laboratory in charge for the study bioanalysis.

CHF6563 blood concentrations will be determined using validated HPLC-MS/MS methods.

The laboratory analysis will be carried out following Good Laboratory Practice (GLP) regulations of the OECD. The analytical procedure will be described in a separate analytical study plan.

7.2.7 Neurological and behavioral assessment

Neurological and behavioral assessment will be performed at the end of treatment period and at 18 months.

At the end of treatment period (48h ±4 h after last dose), general physical and neurological examination will be performed.

At 18 months, cognitive and behavioral development will be assessed using the Bayley Scales of Infant Development– all 5 domains. Moreover, standardized questionnaires will be administered to the mother/primary carer (e.g. Brief Symptom Inventory (BSI), Child Behavior Checklist (CBCL)).

8. EFFICACY ASSESSMENTS

8.1 Primary Efficacy endpoint

Duration of treatment defined as the number of hours from first dose of study drug administration until the last dose of study drug.

8.2 Secondary Efficacy endpoints:

- Time to first weaning, defined as the number of hours from first dose of study drug administration until the first dose reduction
- Requirement for adjunctive drug therapy (phenobarbital) for signs of NOWS
- Total hours of treatment with adjunctive therapy
- Requirement for rescue doses (CHF6563 or morphine)
- Number of rescue doses administered per neonate
- Percentage of total amount of active study drug which is from rescue doses
- Length of opioid related hospital stay, defined as number of days from day of birth until 48 hours after the final dose of drug treatment for Nows
- Relapse of Nows, defined as experiencing recurrence of significant signs of withdrawal
- Incidence of readmissions, defined as readmission to hospital for Nows relapse

Clinical Study Code No.: CLI-06563AA1-02	Version No.: 6.0
IND No.: 131,339	Date: 18 March 2021

9. SAFETY ASSESSMENTS

During administration of sublingual CHF6563 or oral morphine:

- Number and percentage of babies with peri-dosing adverse events (AEs) (i.e., mouth irritation or inflammation, apnoea, desaturation, brady/tachycardia, cough, immediate swallowing of sublingual drug, regurgitation, vomiting occurring after administration)

During the study

From the randomization to the end of the treatment the following information will be collected and presented using summary statistics:

- Adverse events and adverse drug reactions (ADRs).
- Liver enzymes analysis-function testing (AST, ALT,) will be performed on 3 occasions: after the first dose, at stabilization and 48 hours (± 4 h) after the last treatment dose.
- Vital signs: heart rate (HR), respiratory rate (RR), peripheral oxygen saturation (SpO₂), body temperature (BT) will be monitored, and data collected during the escalation and stabilization phases.
- Body Weight and head circumference
- Hematology and blood chemistry: full blood count (FBC), urea, creatinine and electrolytes (sodium, potassium, magnesium calcium, phosphorus), glucose, C-reactive protein if collected before randomization according to site clinical practice.
- Blood pressure (SBP, MBP, DBP) will be monitored according to individual site clinical practice

End of the treatment period

After 48 hours (± 4 h) from the last dose the following will be recorded and presented using summary statistics:

- Vital signs: heart rate (HR), respiratory rate (RR), peripheral oxygen saturation (SpO₂), body temperature (BT). Blood pressure (SBP. MBP. DBP) if collected according to site clinical practice
- Neurological and behavioral assessment
- Body weight, length and head circumference
- All the Adverse Events, and adverse drug reactions, and concomitant medications as well as changes in those already reported.

End of 6 week Follow up

- Signs of / escalation of withdrawal
- All the Adverse Events, and adverse drug reactions, and concomitant medications as well as changes in those already reported.

Follow up to 18 months

- Health status (general medical history and physical examination, including growth parameters, medical illness, developmental issues, medications and hospital admission)
- Environmental / social factors (foster care, domestic violence exposure, substance use / treatment)
- Cognitive and behavioral development (Bayley Scales of Infant Development - all 5 domains)
- Assessments of the mother / primary carer using standardized questionnaires (e.g. Brief Symptom Inventory (BSI), Quick Inventory of Depressive Symptomatology (QIDS), Parenting Stress Index (PSI), Child Behavior Checklist (CBCL))

10. ADVERSE EVENT REPORTING

10.1 Definitions

An **Adverse Event** is “any untoward medical occurrence in a patient or clinical trial subject administered a medicinal product and which does not necessarily have a causal relationship with this treatment”.

An adverse event can therefore be any unfavorable and unintended sign (including abnormal laboratory finding), symptom, or disease temporally associated with the use of a medicinal product, whether or not considered related to the medicinal product.

An **Adverse Drug Reaction** is an “untoward and unintended response to an investigational medicinal product related to any dose administered”.

All adverse events judged by either the reporting Investigator or the Sponsor as having a reasonable causal relationship to a medicinal product qualify as adverse reactions. The expression “reasonable causal relationship” means to convey in general that there are facts (evidence) or arguments meant to suggest a causal relationship.

The definition covers also medication errors and uses outside what is foreseen in the protocol, including misuse and abuse of the product.

A **Serious Adverse Event (SAE)/Serious Adverse Drug Reaction** is any untoward medical occurrence or effect that at any dose falls in one or more of the following categories:

- Results in death

Death is not an adverse event but an outcome. It is the cause of death that should be regarded as the adverse event. The only exception to this rule is “sudden death” where no cause has been established; in this latter instance, “sudden death” should be regarded as the adverse event and “fatal” as its reason for being serious.

- Is life-threatening

Life-threatening refers to an event in which the subject was at risk of death at the time of the event (e.g., aplastic anaemia, acute renal failure, and anaphylaxis). The term does not refer to an event which hypothetically might have caused death if it were more severe.

- Requires hospitalisation or prolongation of existing hospitalisation

Hospitalization refers to a situation whereby an AE is associated with unplanned formal overnight admission into hospital, usually for purpose of investigating and/or treating the AE. Hospitalization for the treatment of a medical condition that occurs on an “elective” or “scheduled” basis or for a pre-existing condition that did not worsen during the study should not necessarily be regarded as a AE. Complications that occur during the hospitalisation are AEs. If a complication prolongs hospitalisation, the event is an SAE. Emergency room visits that do not result in a formal admission into hospital should be evaluated for one of the other seriousness criteria (e.g., life-threatening; persistent or significant disability or incapacity; medically significant).

- Results in persistent or significant disability or incapacity.

The term significant disability should be viewed as any situation whereby an AE has a clinically important effect on the subject’s physical or psychological well-being to the extent that the subject is unable to function normally.

- Is a congenital anomaly or birth defect

- Is a medically significant adverse event

This criterion allows for any situations in which important adverse events/reactions that are not immediately life-threatening or do not result in death or hospitalisation may jeopardise the subject’s health or may require intervention to prevent one of the above outcomes.

Clinical Study Code No.: CLI-06563AA1-02	Version No.: 6.0
IND No.: 131,339	Date: 18 March 2021

Examples of such events are: intensive treatment in an emergency room or at home for allergic bronchospasm; blood dyscrasias or convulsions that do not result in hospitalisation; or development of drug dependency or drug abuse.

Medical and scientific judgment should be exercised in deciding whether an event is serious because medically significant.

Any suspected transmission via a medicinal product of an infectious agent is also considered a serious adverse reaction.

A Non-Serious Adverse Event/Non-Serious Adverse Drug Reaction is an adverse event or adverse drug reaction that does not meet the criteria listed above for a serious adverse event/serious adverse drug reaction.

10.2 Expectedness

An expected adverse reaction is an adverse reaction, the nature or severity of which is consistent with the applicable reference safety information (Investigator's Brochure for CHF6563 and USPI for Morphine), otherwise it is considered unexpected.

Reports which add significant information on specificity or severity of a known, already documented serious adverse drug reaction constitute unexpected events. For example, an event more specific or more severe than described in the Investigator's Brochure would be considered as "unexpected". Examples of such events are: (a) acute renal failure as a labelled ADR with a subsequent new report of interstitial nephritis and (b) hepatitis with a first report of fulminant hepatitis.

In the event an exacerbation is interpreted as due to lack of efficacy, it should not be classified as drug related.

10.3 Intensity of Adverse Event

The investigator is asked to assess the intensity of all the adverse events and to report them in the eCRF.

The intensity (severity) of a specific event is defined as mild, moderate, or severe; the event itself, however, may be of relatively minor medical significance. This is not the same as "serious," which is based on patient/event outcome or action criteria usually associated with events that pose a threat to a participant's functioning. Seriousness (not severity) serves as a guide for defining regulatory reporting obligations.

Each Adverse Event must be rated on a 3-point scale of increasing intensity:

- **Mild:** asymptomatic or mild symptoms; clinical or diagnostic observations only; no change in baseline age-appropriate behavior (e.g. oral feeding behavior, voluntary movements and activity). The event does not lead to either modification of test treatment dosage or establishment of a correcting treatment.
- **Moderate:** resulting in minor changes of baseline age appropriate behavior; requiring minor changes in baseline care or monitoring (e.g. oxygenation, ventilation, tissue perfusion, metabolic stability and organ functioning). The event leads to a diminution of dosage of the test treatment, or a temporary interruption of its administration or to the establishment of a correcting treatment.
- **Severe:** resulting in major changes of baseline age-appropriate behavior; requiring major change in baseline care or monitoring; requiring major change in baseline care or monitoring (e.g. brief, local, non-invasive or symptomatic treatments). The event causes severe discomfort and it may be of such severity to cause the definitive interruption of test treatment.

For the classification of AEs intensity, the "Development of a neonatal adverse event severity scale through a Delphi consensus approach" article released on September 19, 2019 may be used as a guidance.

Clinical Study Code No.: CLI-06563AA1-02	Version No.: 6.0
IND No.: 131,339	Date: 18 March 2021

Since the above-mentioned guidance is based on a 5-grade table, the following conversion will be performed:

AEs grade 1 → Mild

AEs grade 2 → Moderate

AEs grade 3, 4 and 5 → Severe

In order to guarantee objectivity and consistency in the evaluation of AEs (including classification of intensity), the proposed guidance should be followed in alignment with best medical practice. Moreover, clinical abnormalities and other assessments will be reported as AEs if are judged by the Investigator as being clinically significant.

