3. STUDY DESIGN

This is a randomized, multicenter, double blind, double-dummy, parallel group, controlled study. Fifty-seven neonates with neonatal opioid-withdrawal syndrome (NOWS) with or without other concomitant drug withdrawal syndromes will be randomized to receive CHF6563 or morphine treatment. In order to maintain the blind, a double-dummy design will be used so that the subjects will receive either CHF6563 and morphine matched placebo, or morphine treatment and CHF6563 matched placebo.

The weaning period requires a lower number of weaning steps for CHF6563 compared to morphine. In order to avoid maintaining babies randomized to CHF6563 in the hospital following completion of study drug, only to receive placebo for several days (about 5, depending on the severity of the withdrawal), the unblinded pharmacist will advise the clinical staff that the baby has completed active study treatment following the last active dose of CHF6563 and babies will be eligible for discharge (at least insofar as the clinical trial is concerned) 48 hours after the last active dose. Since the cessation dose will not occur at the same weaning step for the 2 treatment arms, it will be possible to ascertain the treatment for each baby after the weaning step which corresponds to the cessation dose of CHF6563. This is considered a "functional unblinding" since, after this point, it will be possible for members of the blinded team to ascertain the treatment arm.

Prior to the last scheduled dose of CHF6563, all members of the blinded study team will remain completely blinded. Following the last scheduled dose of CHF6563/placebo, members of the blinded study team will not have access to the explicit treatment codes, but it will be possible to ascertain the treatment arm. Similarly, data review will occur without access to explicit treatment codes, since the explicit treatment codes will be maintained in a confidential manner. The randomization list and explicit treatment codes will be disclosed to blinded study team members only after the database is locked.

Clinical Study Code No.: CLI-06563AA1-02	Version No.: 6.0
IND No.: 131,339	Date: 18 March 2021

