12.3.7 Safety variables

Adverse Events

Safety analysis will be based on Safety population. All adverse events starting on or after the time of first study drug intake will be classified as treatment emergent adverse event (TEAE). Any adverse events started after the informed consent signature and before the time of first study drug intake will be classified as pre-treatment adverse events.

The number of babies who experienced at least one TEAE, drug-related TEAE, serious TEAE, serious related TEAE, TEAE leading to study discontinuation, TEAE leading to death, and peri-dosing TEAEs will be summarized by treatment arm. Summaries will be presented overall (number and percentage of babies having at least one event, total number of events) and by system organ class and preferred term (number and percentage of babies having at least one occurrence of that event).

All adverse events will be listed.

Pre-treatment adverse event will be listed only.

The peri-dosing AEs are defined as adverse events occurring during or shortly after administration of study treatment, i.e. within 10 minutes from the start of study drug administration.

Vital signs

Vital signs will be summarized at each planned time point by means of descriptive statistics. At each timepoint when vital signs are collected, mean, min, max and standard deviation of the observed values and change from baseline will be presented, in addition to being listed.

Laboratory data

Sites will use local labs to obtain liver enzymes analysis-function testing. When consistent with site clinical practice, sites will use local labs to collect hematology and blood chemistry. The laboratory values and the change from baseline for continuous laboratory parameters will be summarized by descriptive statistics at each planned time point. All laboratory data will be listed with abnormal values flagged.

Head circumference (and percentile) and body weight (and percentile)

Head circumference (and percentile) and body weight (and percentile) and their corresponding changes from baseline will be summarized using descriptive statistics at each planned time point.

Additional Safety Variables

The following parameters collected only at the end of the treatment period will be listed only:

- Neurological and behavioral assessment

Analysis of safety variables collected at the 18-month follow up visit will be described in the SAP.

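### Does the blurred line between Moderate and Severe adverse events in protocol 10.3 call for a change to the plan?

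*Protocol*

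**What the plan says.** Protocol 10.3 asks the investigator to rate each adverse event on three levels.

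- **Mild** excludes any event that leads to a change of test treatment dosage or to a correcting treatment.
- **Moderate** covers events "requiring minor changes in baseline care or monitoring (e.g. oxygenation, ventilation, tissue perfusion, metabolic stability and organ functioning"). It also covers events leading to a lower dose, "or a temporary interruption of its administration or to the establishment of a correcting treatment".
- **Severe** names major change in behavior and then states the large change in care twice in succession. Only the second statement carries an example: "requiring major change in baseline care or monitoring (e.g. brief, local, non-invasive or symptomatic treatments"). The definition closes with "The event causes severe discomfort and it may be of such severity to cause the definitive interruption of test treatment".

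A published neonatal severity scale is offered as support. Section 10.3 first says that the "article released on September 19, 2019 may be used as a guidance", then fixes a conversion of its five grades (1 to Mild, 2 to Moderate, 3 to 5 to Severe), and later says that "the proposed guidance should be followed in alignment with best medical practice".

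On reporting, protocol 12.3.7 lists the planned adverse event categories, ending with "TEAE leading to study discontinuation, TEAE leading to death, and peri-dosing TEAEs will be summarized by treatment arm"; none of them uses intensity. SAP 3.1.1 takes severity as collected. SAP 3.1.3 adds a row for severe treatment-emergent events to the overview table (Table 14.3.1.1), and SAP 8.2 adds listing 16.2.7.7.

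**The concern.** The example under Severe describes light treatment, while the criterion it illustrates is a large change in care. Moderate already includes events that need a correcting treatment, a term section 10.3 does not define. A baby given a short symptomatic treatment could thus be graded Moderate by one investigator and Severe by another. The organ-function examples appear only under Moderate, which might pull some events the other way. The external scale that could settle such cases is optional in one sentence and expected in another.

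Safety and tolerability is a primary objective (protocol 2.1, SAP 1.1), and the SAP states no adjudication of the grade. Inconsistent grading would pass straight into the severe-event row, which is shown by treatment.

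**Working it through.** No figure in the plan is at issue, so the check sets the definitions side by side and then follows the grade into the outputs.

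**1. Where a briefly treated event falls.** Suppose the treatment counts as a correcting one.

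| Grade | Relevant element | Met? |
|---|---|---|
| Mild | no correcting treatment | no, so excluded |
| Moderate | correcting treatment started | yes |
| Severe | example of a large change in care | yes, by the example |
| Severe | major behavior change; severe discomfort | not implied by brief treatment |

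Section 10.3 does not say whether the elements of a grade are alternatives or are required together. If they are alternatives, the event fits both Moderate and Severe. If they are required together, an event without major behavior change and severe discomfort is Moderate. The double fit is possible, not certain.

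**2. The organ-function examples.** They can be read as areas of care in which the change is small. The qualifier still governs, so a large change in ventilation support does not become Moderate through its mention there.

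**3. The guidance.** The two statements differ in strength, but neither makes the scale mandatory, and the five-to-three conversion is fixed. The article is not in the documents, so whether it removes the overlap cannot be checked.

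**4. Where the grade is used.**

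- SAP 3.1.3 overview table: 13 rows (treatment-emergent, serious, non-serious, drug reactions, serious reactions, severe, leading to drug discontinuation, leading to death, peri-dosing, reactions leading to discontinuation, reactions leading to death, peri-dosing reactions, post-treatment). Selected by severity: 1.
- SAP 8.2 adverse event listings 16.2.7.1 to 16.2.7.10: 10. Selected by severity: 1.
- Protocol 12.3.7 categories: 7 (treatment-emergent, drug-related, serious, serious related, leading to study discontinuation, leading to death, peri-dosing). Selected by severity: 0.

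Protocol 10.2 (expectedness) and 10.8 (follow-up of unrelated serious events) also mention severity, but neither says that the three-point grade drives those decisions. Section 10.3 ties regulatory reporting to seriousness.

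**5. How far one doubtful grade could move the row.** SAP 5.4.1 uses all subjects in the analysis set and phase as denominator. With 7 babies randomized (SAP 6.1), no arm exceeds 7. If one grade alone decides whether a baby has any severe event, that arm's percentage moves by at least 1/7 = 14.3 points. The actual split is not given. Assuming 5 and 2, the nearest whole split to 2:1 (7 × 2/3 = 4.7; 7 × 1/3 = 2.3), the shift is 1/5 = 20 points or 1/2 = 50 points. This is conditional arithmetic and does not show that any event was misgraded.

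**6. What a change could achieve.** Rewording section 10.3 cannot reach grades already given in a terminated trial. Re-grading could introduce bias, because under protocol section 3 "it will be possible to ascertain the treatment for each baby after the weaning step" at which CHF6563 ends. A footnote would disclose the ambiguity but leave every count as it is.

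**The case for a change.** The strongest case for acting is that the defect is plain on the page and the remedy is cheap. Table 14.3.1.1 is the only safety table left in the reduced SAP, the severe-event row is shown by treatment, and at this sample size one grade moves a percentage visibly. Without a footnote, a reader may take the row as a cleanly defined grade. Section 10.3 itself gives objectivity and consistency as the aim of the guidance, and optional wording works against that aim.

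Much of this stands. The example is misplaced or incomplete, the clause is duplicated, and the two statements on the guidance differ. The sensitivity in step 5 is also correct as arithmetic.

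It does not carry the conclusion. A percentage based on at most 7 babies cannot support a comparison of severity between arms whatever the grading rule, and SAP 6.1 already says that the objectives are not evaluable. Listing 16.2.7.2 shows all collected information on every treatment-emergent event, so a reader can examine individual cases. A note that severity is the investigator's rating would repeat section 10.3. That section also allows an intense event to be of minor medical significance, which softens the clash between Severe and light treatment.

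**Conclusion.** No change to the plan follows, because none would bring a gain. Section 10.3 contains a drafting inconsistency of low importance: an ill-fitting example, a repeated clause, and two strengths of wording for the same guidance. It creates a double fit only if the elements of a grade are alternatives. Among the SAP outputs, the grade selects one overview row and one listing; efficacy and seriousness-based reporting do not depend on it.

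This rests on three facts in the SAP: 7 babies randomized, termination in February 2022, and no statistical analysis of the collected data. It also rests on leaving recorded grades as they stand. The number and direction of any doubtful grades are unknown, since no adverse event counts are given. Had the trial continued to 57 babies, clarifying the scale would have been worthwhile. If it is reused elsewhere, the Moderate and Severe definitions and the two statements on the guidance would need to be reconciled; the documents do not show which wording was intended.
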